9.4. Responsibilities for Reporting Serious Adverse Events

The Investigator will record all serious adverse experiences that occur during the study period in the appropriate source documents and/or AE log as applicable. The study period for reporting serious adverse events will be from the time of signing consent to final study visit.

As sponsor of the relevant IND, the PI is responsible for compliance with the FDCA (21 USC §§ 301 e. seq.) as well as the implementing regulations [Title 21 of the CRF]. These responsibilities include reporting any unexpected fatal or life-threatening suspected adverse reactions to the FDA/CDER no later than 7 calendar days after initial receipt of the information.

Additionally, the PI will comply with all federal regulations and RSRB policies regarding the reporting of adverse events.

10. RISK/BENEFIT ASSESSMENT

10.1. Potential Risks

Exacerbation of heart failure symptoms, fluid retention, pedal edema and weight gain are the primary risks of concern in this study. Similarly, fluid retention may cause anemia by diluting the blood. Liver problems have been reported in some patients receiving pioglitazone in the presence of active liver disease. Recent evidence links prolonged pioglitazone treatment (>1 year) in diabetics with increased risk of bladder cancer (from 7/10,000 to 10/10,000). Our subjects will be

treated for a maximum of 6 months. Additionally, by excluding subjects with a history of bladder malignancy we are following the FDA advice to not begin this medication in subjects with a past or present history of bladder cancer. Similarly, our subjects will not be on pioglitazone long enough to increase their risk of bone fractures. While subjects with diabetes have experienced macular edema and low blood sugar, these potential adverse effects are markedly less common in nondiabetics. Women with polycystic ovarian syndrome may have their ovulation cycles normalize.

As with other drugs, some patients may develop an allergic reaction to pioglitazone. Minor risks associated with pioglitazone treatment included headache, sinus infection, muscle pain, sore throat, tooth disorders and respiratory tract infections.

For full details, please see the attached package insert.

10.2. Protection Against Risks

Patients will be advised of possible drug side effects by study personnel and encouraged to contact the study coordinator if they suspect side effects are occurring. Risks will be minimized by 1) good case selection 2) education and 3) stopping drug treatment when significant side effects are identified. Appropriate screening of subjects for subclinical side effects of Pioglitazone will also minimize risk. Since the drug's side effects are not abrupt in their onset, the followup included in the study design should be effective. Should side effects be noticed, patients will be treated by study personnel and counseled, or referred to their provider.

10.3. Potential Benefits to Subjects

Subjects may benefit from reduced numbers of tumors if drug treatment works as expected.

10.4. Alternatives to Participation

No research alternatives are available to the subject, and they can pursue usual care.

11. CONFIDENTIALITY OF DATA AND INFORMATION STORAGE

Confidentiality of protected health information and samples is ensured through the following measures:

- Only authorized persons will be granted access;
- Only authorized persons may enter and view study data;
- Passwords and system IDs will not be shared;
- Physical security of the workstations/files will be maintained;
- Adequate back-up plan is in effect;
- Staff trained on data entry system and importance of security procedures;
- Workstations with databases will not be left unattended while in use, and will be left locked and password protected.
- Only study team members will have access to subject identifiers. Samples and data will be labeled with unique, random codes.
- Codes will not be generated from existing identifiers, such as initials or enrollment date.
- A link will be maintained indefinitely between subject identifiers and the codes.
- The link will be stored on a password-protected computer, accessible only to study team members.

12. RESEARCH INFORMATION IN MEDICAL RECORDS

Blood test results will be in the patients' medical record for medical reasons unrelated to Pioglitazone treatment, as will results of biopsies as needed for normal patient care. No other study information will be in the medical record.

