2.3. Rationale for Dosage

Subjects will be treated with Pioglitazone 30 mg po daily when on treatment, following an initial 2 week period to assess tolerability, particularly in patients with stage 1 or stage 2 heart failure. Pioglitazone was selected because of our recent investigations showing its profound efficacy in decreasing proliferation in human SCC in vitro (see BACKGROUND). The oral dose selected results in serum levels of Pioglitazone that correspond to the in vitro dose tested in our studies(Christensen *et al.*, 2005). In addition to the drug itself acting as an agonist for PPAR γ , there are 2 persistent metabolites that have similar agonist effects, increasing the possibility of tumor growth inhibition. Thus, this dosing regimen is likely to give optimal suppression of tumor growth. This is a standard dose (30 mg) taken by patients who are taking Pioglitazone for management of their diabetes. When given to non-diabetic patients with non-alcoholic liver disease or those with hepatitis C to prevent cirrhosis(Bell *et al.*, 2012), there were no untoward effects on glucose metabolism.

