5.2. Safety Assessments

The main safety issue associated with this trial is whether an adverse effect will occur in patients due to the administration of pioglitazone. Clinical endpoints to monitor for safety are: weight, pedal edema, dyspnea, heart failure, headache, myalgia, fracture, liver injury and vision changes related to macular edema, blood in the urine or other changes that are out of the ordinary. The study related blood monitoring is to ensure there are no preexisting conditions that make participants susceptible to drug-related side effects. For instance, individuals with preexisting liver disease may have hepatotoxicity when taking pioglitazone, hence they must be excluded from participation. However, since participants could develop new diseases while participating, blood will also be taken from subjects taking pioglitazone to screen for such concerns. At a study visit approximately 60 days after drug initiation, blood work will be repeated to detect changes suggesting drug related side effects. Monitoring of blood for glucose levels, altered liver function, or decreased Hemoglobin could indicate the patient should stop taking the study drug. Tests to be followed will be CBC and CMP at baseline, approximately 60 days after starting drug and at the end of treatment. Blood test results will be interpreted in the context of the clinical exam. The patient population being studied has co-morbidities that require them to regularly give blood to monitor their health as part of their routine care, so study related blood draws may not be necessary if these tests are obtained by their providers at appropriate intervals; it will not be necessary to repeat them. The risk of bladder cancer will be monitored by urinalysis. Taking Pioglitazone for > 1 year increases the risk of bladder cancer from 7 in 10,000 to 10 in 10,000. Female patients of child bearing age will have urine pregnancy testing at baseline and at subsequent study visits. **Stop Criteria:** Subjects will be

dropped from the protocol if clinical or laboratory assessment reveals grade II abnormalities as defined by Common terminology Criteria for adverse events V.3. Subjects will also be dropped from the protocol if they are unable to tolerate 30 mg Pioglitazone treatment when the dosage is increased to 30 mg daily after the initial 2 week treatment with 15 mg daily.

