5.3. Assessment of Subject Compliance

The study coordinator will assess the subject's compliance with the protocol by counting the pills remaining in the prescription obtained for the study. The date the prescription was filled relative to the study visit date will also be noted.

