5.6. Costs to the Subject

Subjects will be prescribed Pioglitazone, a drug that costs \$12 per month. The cost of drug will be paid by the Department of Dermatology. Costs of blood tests specifically related to the study to monitor safety of drug administration are also covered by the department. The costs related to subject's cancer treatment (standard care) will be charged to insurance as is routine. There is only Department of Dermatology clinical grant support for this project for coverage of medication costs.

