8.4. Accountability of Investigational Supplies

The study drug is ordered through the investigational drug service. The study drug will be dispensed to the Study Coordinator and transported to the Red Creek clinic site of [name]. It will be stored in a locked cabinet at room temperature until the supply is given to the patient for use. Once patients give consent, the study drug will be dispensed when patients enter the active treatment arm of the protocol. On return appointment, patients will bring their study drug bottle with them. A pill count will be done at each study visit, and the date of drug dispensing will be noted. At the visit prior to completion of the active treatment arm, the exact number of pills required for the planned period until the next study visit will be dispensed to the patient. This will facilitate having patients stop taking drug at the same time as their last “on treatment” study visit.

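### Section 12, read as written, keeps pioglitazone exposure out of the medical record, and the protocol text requires no notice to the usual provider when the drug starts (low severity)

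*Combined protocol and SAP*

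**What the plan says.** Section 12 of the combined protocol and SAP is short. It places blood test results in the medical record, which it describes as being there for reasons that have nothing to do with pioglitazone, along with biopsy results from ordinary care. It closes with the rule that "No other study information will be in the medical record".

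Section 5.2 describes who these patients are: "The patient population being studied has co-morbidities that require them to regularly give blood to monitor their health as part of their routine care". It adds that "study related blood draws may not be necessary if these tests are obtained by their providers at appropriate intervals". The plan thus expects other clinicians to be seeing and testing these subjects during the trial.

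Section 3.2 excludes heart failure only in NYHA classes III and IV. Section 2.3 introduces the two-week tolerability period with milder disease in mind, "particularly in patients with stage 1 or stage 2 heart failure". Section 10.1 names worsening heart failure, fluid retention, edema and weight gain as the main risks, and adds anemia through dilution of the blood.

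Contact with a subject's own physician appears in two places. Section 5.8 has significant side effects attributed to the drug reported to the physician. Section 10.2 has study staff treat a side effect or refer the subject to the provider once it is noticed.

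**The concern.** The main toxicities of pioglitazone look like common problems in older patients with other illnesses. Edema, breathlessness and a falling hemoglobin have many causes, and a clinician needs to know about the drug to put it on the list. If the chart is silent, recognition depends on the patient volunteering the information at a visit that study staff did not arrange. A drug effect could then be worked up as something else, and stopping the drug could be delayed.

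What is at stake is the timely recognition of adverse effects in routine care. The tumor counts, the sample size and the planned models do not depend on it.

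**Working it through.** No arithmetic applies, and the plan states no figure to reproduce. The check is to set Section 12 against every other section that could put the drug in the chart or tell an outside clinician about it.

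1. **Section 12.** Two items are admitted and everything else from the study is excluded. Drug exposure is not one of the two. The only mention of pioglitazone is to say that the blood results are there for unrelated reasons.

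2. **Drug supply (Sections 5.3, 5.6, 8.1, 8.4).** These sections cover ordering, cost, storage, dispensing and pill counts. None says that an order or a medication-list entry will be made in the chart.

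3. **Adverse event recording (Sections 9.3, 9.4).** Events are documented by the study, and serious events go into source documents or an adverse event log. The medical record is not named as a required place for the drug or its dates.

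4. **Contact with physicians (Sections 5.8, 10.2).** Both routes open only after a side effect has occurred and study staff know of it. Neither applies on the day the drug starts.

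5. **Oversight (Section 13.3).** The investigators and the safety monitor review events that reach them. This does not inform the treating clinician.

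6. **Recruitment (Section 4.1).** The coordinator reviews EPIC records to find candidates, so the study team already works in the chart. The letter to outside dermatologists and surgeons is a recruitment tool and says nothing about subjects who have started treatment.

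The clinical consequence follows from the protocol's own statements. Other providers see these subjects (5.2), milder heart failure is admitted (2.3, 3.2), and the listed risks are non-specific (10.1). Both randomized sequences receive pioglitazone (13.1), so the rule covers every treated subject. That describes the scope of the rule and is no measure of risk. The documents give no rate of outside encounters and no rate of late recognition, so the risk cannot be calculated.

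Two parts of the study are untouched. Study staff know who is on drug, so their own use of provider laboratory results is sound. A referral that study staff make can carry the information with it. The gap is confined to encounters that study staff did not start.

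**The case against.** The strongest reply is that Section 12 concerns research data. Its title refers to research information, it follows the confidentiality section, and its closing sentence may have been meant only to keep markers and codes out of the chart. Reporting side effects to physicians (5.8) and referring patients (10.2) do not suggest an intention to hide the drug. This reading is possible, but no exception for the drug is written anywhere, and staff who follow the sentence literally would leave the drug out.

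A reader could also argue that an ordinary prescription would create a chart entry in any case. Section 5.6 says "Subjects will be prescribed Pioglitazone" and Section 5.3 measures compliance by "counting the pills remaining in the prescription obtained for the study". Section 8.4, however, says "The study drug is ordered through the investigational drug service" and "The study drug will be dispensed to the Study Coordinator". None of this addresses charting, so it neither rescues Section 12 nor proves that no order would appear. A reader might infer a substantive contradiction in how the drug is supplied. That goes too far, because the passages may be loose wording for one process, and aligning them would be editorial.

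The safeguards are real. Treatment is open label, so patients know what they take. NYHA class III and IV heart failure, problems with pedal edema, liver disease and past bladder cancer are excluded (3.2). Dosing starts at 15 mg for two weeks (8.2). Subjects are asked directly about adverse experiences and have urine checked for blood at each study visit (9.3). They are encouraged to call the coordinator, and the side effects are described as gradual in onset (10.2). These points lower the risk and justify a low rating. They do not inform a clinician whom the patient sees between study visits.

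Finally, Appendix 1 and the consent pages were not in the text available. A provider letter or wallet card may be described there, and its absence is not claimed.

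**Conclusion.** The point holds at low severity. Section 12, as worded, excludes pioglitazone exposure from the medical record, and nothing in the protocol text available makes an exception or requires notice to the usual provider at drug start. The consequence is a modest risk, which cannot be quantified, that a drug effect is recognized late when a subject sees a clinician outside the study and does not mention the drug.

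This rests on the plain reading of Section 12 and on Appendix 1 and the consent form containing no provider notice. If they do contain one, most of the safety consequence falls away and what remains is a sentence to clarify.

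A reader might go further and infer that the plan conceals the drug from treating clinicians, that safety monitoring within the study is compromised, or that the results are at risk. The documents support none of these. Sections 5.8 and 10.2 provide for contact with physicians, Section 9.3 provides for monitoring at study visits, and the primary endpoint and its analysis do not draw on the missing chart entry.

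**What to change.** Amend Section 12 so that the medical record will show study participation, pioglitazone with its start and stop dates, and a route for contacting the study. Research tumor markers and study codes stay out, which leaves the confidentiality measures in Section 11 intact. The drug entry should be dated from when the drug begins. For subjects who start with usual care, that is the crossover to pioglitazone and not enrolment.

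Notify the usual provider when the drug starts, unless Appendix 1 or the consent form already arranges this. The notice matters because the documents do not say that subjects' other providers use EPIC, so a chart entry alone may not reach them.

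The cost is a reworded section, a sentence in the consent form, one chart entry per subject and, if not already planned, one notice per subject. The downside is small: participation becomes visible to treating staff, and the consent must say so.

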13. DATA ANALYSIS AND MONITORING

13.1. Sample Size Determination

[figure not shown]
This pilot study will be designed as a 2-by-2 crossover trial. We refer to Section 2.2 for a justification of the study design. Patients will be enrolled and randomized in one arm of two treatment protocols. Each protocol will include two treatments administered during two consecutive time periods:

- Treatment arm # 1: Patients enrolled in the first arm will first receive six months of usual care (*Period 1*); next, they will be treated with Pioglitazone combined with usual care for the next 6 months (*Period 2*). Patients will take study drug until they come to their final “on Treatment” visit, which will occur 168 days +/- 14 days of their “on Treatment” date.
- Treatment arm # 2: Patients enrolled in the second arm will first receive six months of Pioglitazone treatment combined with usual care (*Period 1*); next, they will receive usual care alone during the following 6 months (*Period 2*). Patients will take study drug until they come to their final “on Treatment” visit, which will occur 168 days +/- 14 days of their “on Treatment” date.

A flow diagram describing the study design is presented in Section 2.

The primary endpoint will be the total number of skin tumors counted during each treatment period. Based on clinical evidence, we expect the total number of skin tumors to range between 0 and 3 per patient and per treatment period (or 0 to 6 per patient per year) and to average around 1.5. We would consider Pioglitazone to be clinically effective if it reduces tumor counts by 50% (that is, reduce the average number of tumors from 1.5 to 0.75 per patient and per treatment period). Previous work by this investigator has shown that such reductions in tumor numbers can occur when prostaglandin metabolism is affected by drug treatment (Elmets *et al.*, 2010).

A two-sided *t*-test achieves 96% power to detect a reduction in the number of skin tumors due to Pioglitazone when the total sample size of a 2-by-2 crossover design is 40 (20 patients per group). The calculations assumed that the actual mean difference is 0.75 (corresponding to a 50% reduction in the mean number of skin tumors due to treatment), the square root of the within mean square error is 1, and the significance level is 5%. The figure below displays the power of the study as a function of the sample size (N) for three values of the square root of the within mean square error (SW).

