13.2. Planned Statistical Analysis

The main objective of the statistical analysis will be to estimate the effect of Pioglitazone on the occurrence of skin tumors when used in combination with usual care compared to usual care alone. The primary endpoint will be the total number of skin tumors counted during each treatment period. We will have two observations per patient, one for each treatment period of the 2-by-2 cross-over design (either baseline to 6 months, or 6 months to 12 months post-baseline). We will first compute the empirical mean (and its standard error), standard deviation and median for the number of skin tumors within each treatment arm and each treatment period. We will also construct histograms for tumor counts. We expect tumor counts to range between 0 and 6 per six months, such that parametric mixed analysis of variance (ANOVA) may not be the most appropriate approach to assess treatment effects. As an alternative, we will describe the number of skin tumors using log-linear Poisson regression models with random effects. The developed models will include treatment arm, period, and their interaction as covariates while adjusting for potential intra-subject dependencies (or between subject variation) using random intercepts. We will use this model to investigate the presence of washout effect (secondary aim).

In additional, exploratory analyses, we will assess if the phenotype of skin tumors changes during treatment with Pioglitazone. We will also determine if Pioglitazone changes the expression of markers influenced by PPAR γ or AKR1C3 (apoptosis, proliferation) in tumors removed from treated patients. We will have an apoptosis and a proliferation score for every skin tumor that arises, both treated as continuous variables. The analyses will be conducted using mixed ANOVA modeling the apoptosis and the proliferation scores of each tumor as a function of treatment arm,

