period, and their interaction. Random intercepts will also be included in the models to account for subject to subject variability. We will develop separate models for the apoptosis and for the proliferation scores. We will investigate modeling assumptions using plots of residuals and conditional residuals. In the event modeling assumptions appear violated, we will consider applying suitable transformations (e.g., logarithmic, square root) to normalize the data. As an alternative, we will consider performing statistical inference using a generalized estimating equations (GEE) approach.

All tests and construction of confidence intervals will be two-sided and conducted at the 5% significance level.

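### Section 13.1 states 96% power, but its own inputs give 90.5%, and Sections 13.1 and 13.2 give different expected tumor counts for the same six months

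*Combined protocol and SAP*

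**What the plan says.** Section 13.1 sets the trial up as a randomized 2-by-2 crossover, with the number of skin tumors in each six-month period as the primary endpoint. It gives a two-sided t-test, 40 patients in total (20 per sequence) and a mean difference of 0.75 tumors, from 1.5 to 0.75 per patient per period. It also assumes that "the square root of the within mean square error is 1, and the significance level is 5" percent. From these it reports that the test "achieves 96% power to detect a reduction in the number of skin tumors due to Pioglitazone". A figure, not reproduced in the text available for this review, plots power against sample size for three values of Sw.

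Section 13.2 confirms the sidedness: "All tests and construction of confidence intervals will be two-sided and conducted at the 5% significance level".

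On expected counts, Section 13.1 says "we expect the total number of skin tumors to range between 0 and 3 per patient and per treatment period", and equates this to 0 to 6 per year. Section 13.2 says "We expect tumor counts to range between 0 and 6 per six months".

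**The concern.** All the inputs needed to recompute the power are printed, and they do not lead to 96%. At least one printed entry must therefore be wrong: the power, Sw, the difference, the sample size or the sidedness. The prose does not show which.

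The power statement is the numerical justification for 40 patients, and Sections 2.1 and 2.2 say that the pilot will inform a larger multicenter trial. A misprinted Sw or a one-sided calculation could carry over into that later sample size.

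The two count ranges describe the same endpoint over the same length of time, yet their upper limits differ by a factor of two. The plan gives no source for Sw = 1, so a reader who wants to judge that value against the expected spread of counts has two conflicting descriptions to work from.

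**Working it through.** **Inputs, all from Section 13.1:** N = 40 (20 per sequence), difference 0.75, Sw = 1, two-sided alpha 0.05.

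**Power from the printed inputs**

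- Standard error of the treatment difference in a balanced 2-by-2 crossover: Sw × √(2/N) = 1 × √(2/40) = 0.2236.
- Noncentrality: 0.75 / 0.2236 = 3.354.
- Degrees of freedom: N − 2 = 38.
- Two-sided 5% power from the noncentral t distribution: 0.9046, or 90.5%. The normal approximation gives 91.8%.
- A simulation of 200,000 crossover trials with normal errors, Sw = 1 and 20 per sequence gave 0.905.

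The type II error is 1 − 0.905 = 9.5%, against 1 − 0.96 = 4% as stated.

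**Attempts to reproduce 96%**

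| Reading | Power | Agrees with the text? |
|---|---|---|
| Two-sided 5%, t, 38 df | 90.5% | Yes |
| Two-sided 5%, normal approximation | 91.8% | Not a t-test |
| One-sided 5%, t | 95.0% | No, the test is two-sided |
| One-sided 5%, normal approximation | 95.6% | No, the test is two-sided |
| Sw taken as the SD of the within-patient difference | 99.6% | No, Sw is defined as the root within mean square error |
| Parallel groups of 20 | 63.7% | No, the design is a crossover |

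The one-sided normal approximation is the only reading in the table that rounds to 96%, and it contradicts the stated test.

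**What would give 96% with a two-sided 5% t-test, changing one input at a time**

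- Sw = 0.881, or
- a difference of 0.852, or
- N = 51 (0.960), which means 52 with equal groups (0.963). N = 50 gives 0.957, which also prints as 96%.

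**Sample sizes around 40, with difference 0.75 and Sw = 1:** N = 38 gives 88.9%, N = 39 gives 89.7% and N = 40 gives 90.5%.

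**Sensitivity to the count range.** This rests on an assumption that the plan does not make: Poisson-shaped counts, cut off at the top of the stated range, with means held at 1.5 and 0.75. Sw is the square root of the average of the two variances, and power is for the t-test with N = 40.

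| Range per six months | Variances (usual care, pioglitazone) | Sw | Power |
|---|---|---|---|
| 0 to 3 (Section 13.1) | 0.982, 0.686 | 0.913 | 94.7% |
| 0 to 6 (Section 13.2) | 1.476, 0.750 | 1.055 | 87.3% |
| No upper limit | 1.5, 0.75 | 1.061 | 86.9% |

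Under this assumption the choice between the two stated ranges moves power by 94.7 − 87.3 = 7.4 points, and neither range reaches 96%.

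**The case against.** The strongest case on the other side accepts the arithmetic and disputes how much it matters.

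- **The missing figure.** The power figure in Section 13.1 could not be read here and may show which entry was intended. That is correct, so the statement that the wrong entry cannot be identified applies to the prose only. The prose would still need to be corrected to match.
- **Rounding.** A printed 96% covers anything from 95.5% upward. On that basis N = 50, an Sw up to about 0.894 or a difference from about 0.839 would be enough. This is fair, but none of these is the printed value.
- **The count ranges are not inputs.** Sw = 1 is stated directly, and Section 13.2 uses its range only to explain why ANOVA may be unsuitable. An expected range is also not a cut-off point, and Sw = 1 lies between the two values in the sensitivity (0.913 and 1.055). This stands as a limit on the 7-point figure, which is illustrative. It does not remove the contradiction between the ranges.
- **The planned model is different.** Section 13.2 plans a Poisson regression with random effects, so neither 4% nor 9.5% is the error rate of that analysis. Also true: both figures describe the t-test calculation that the plan printed.
- **Low consequence.** This is a feasibility pilot, Section 2.2 also ties its size to local recruitment, and the plan never sets 90% as a target. This supports keeping N = 40. It is no reason to leave a wrong power figure in the plan.

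**Conclusion.** The concern holds. With the inputs printed in Section 13.1 the power is 90.5%, not 96%, and the type II error is 9.5%, not 4%. This rests only on the plan's own numbers and the standard t-test for a balanced 2-by-2 crossover. No reading consistent with the stated two-sided 5% test gives 96%. The expected counts for a six-month period also conflict: 0 to 3 in Section 13.1 and 0 to 6 in Section 13.2.

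The error does not undermine the sample size. Forty patients still give just over 90% on the printed inputs, although 40 is the smallest total that does so. Which entry was misprinted cannot be settled from the text. The effect of the count range on power depends on an assumed Poisson shape and should be read only as an indication. This should be fixed, but it is not a fatal fault.

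**What to change.** 1. Rerun the power calculation in Section 13.1. If Sw = 1 and the two-sided 5% test are as intended, change the stated power from 96% to 90%. If another entry was misprinted, correct that entry instead.
2. Check the result against the power figure in Section 13.1 and make the text and figure agree.
3. State one expected range of tumor counts per six months in both Sections 13.1 and 13.2, and add one sentence on why the chosen Sw fits it.
4. Keep N = 40.

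The cost is one rerun and a few words in two sections. The stated power will probably look slightly less favorable. There are no extra patients and no change to design, conduct or analysis.
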